Ceralasertib dosing				← Dosing on Days 1-7 only →	
Medication dispensed/returned/medication accountability	X			X	X
Survival					X

^a Treatment allocation will be randomised. It is recommended that patients commence study treatment as soon as possible after randomisation, and ideally within 3 days.

^b If assessment done within 7 days before starting study treatment, does not have to be repeated on Day 1 of study treatment unless the Investigator believes results have changed significantly.

^c Safety blood samples do not need to be repeated on Day 1 of study treatment if assessed at least 3 weeks after the last dose of chemotherapy but within 7 days before starting study treatment, unless the Investigator believes that it is likely to have changed significantly. Coagulation test should be performed if clinically indicated. Safety blood tests must be reviewed prior to dose administration. For a list of all required laboratory tests please refer to Section 5.2.1.

^d Physical examination should be done as per schedule but does not need to be recorded in the eCRF after the baseline assessment (except for weight which should be collected at each visit). Any clinically significant changes not unequivocally related to disease progression should be recorded as AEs.

- e RECIST 1.1 follow-up assessments will be performed every 8 weeks (± 1 week) for the first 72 weeks, then every 12 weeks (± 1 week) after randomisation until objective disease progression as defined by RECIST 1.1, irrespective of treatment decisions. Any patient who has not yet shown objective radiological disease progression at withdrawal from IP should continue to be followed as per RECIST 1.1. Follow-up assessments will include CT assessments of chest, abdomen and pelvis (or MRI where CT is contraindicated) for all patients. Any other sites at which new disease is suspected should also be appropriately imaged. If an unscheduled assessment was performed and the patient has not progressed, every attempt should be made to perform the subsequent assessments at their scheduled visits.
- f ECG assessment to be done on Day 1 of every cycle, within 1-2 hours prior to dosing. An additional baseline assessment will be conducted on Day 1, Cycle 1.

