5.1 Efficacy assessments

5.1.1 CT and MRI scans; Tumour assessments (RECIST 1.1)

Following the baseline assessment, subsequent tumour assessments according to RECIST 1.1 should be performed every 8 weeks (± 1 week) for the first 72 weeks and then every 12 weeks (± 1 week) thereafter, relative to the date of randomisation and irrespective of treatment decisions, up to objective disease progression by RECIST 1.1.

The imaging modalities used for RECIST 1.1 assessment will be CT scans of the chest, abdomen and pelvis (or MRI where CT is contraindicated) with other regions as clinically indicated for the assessment of disease. Brain CT scan/MRI at baseline should be done for patients with known history of brain metastatic disease. Any other sites at which new disease is suspected should also be appropriately imaged. The methods of assessment of tumour burden used at baseline must be used at each subsequent follow-up assessment.

Radiological examinations performed in the conduct of this study should be retained at site as source data.

Coded copies of all scans, regardless of modality, are to be sent to an AstraZeneca appointed CRO for BICR.

All treatment decisions will be based on site assessment of scans. After the primary PFS analysis for each of the strata, central review of scans will no longer be required for that stratum and Investigators will be advised when to stop sending copies of the scans to the CRO conducting the central review. Patients who are determined to have progressed according to RECIST 1.1 criteria by the Investigator will have scans centrally reviewed for confirmation of objective disease progression. If disease progression is not confirmed at central review an additional RECIST 1.1 assessment may be requested preferably at the next scheduled RECIST 1.1 visit, if the central assessment is available in an appropriate timeframe.

It is important to follow the assessment schedule as closely as possible. If scans are performed outside of scheduled visit ± 1 week window interval and the patient has not progressed, every attempt should be made to perform the subsequent scans at their scheduled time points. Patients will be evaluated until objective radiological disease progression by RECIST 1.1 as per the study schedule (see [Table 3](#), and [Table 4](#) and [Table 5](#)), and then followed for survival, regardless of whether study treatment is discontinued or delayed and/or protocol violations, unless they withdraw consent.

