Non Progressive Disease (Futility Interim only)

NPD will be assessed 8 weeks after dosing and is defined as the proportion of all patients dosed that have a visit response of SD, PR or CR at Week 8. Earlier visit responses of CR, PR that become PD at Week 8 or NE responses at Week 8 do not constitute NPD at 8 weeks.

A time window around the Week 8 visit will be applied, such that any visits occurring 7 weeks or more after dosing are acceptable; however, if an earlier visit is defined as PD then the visit response at Week 8 would also be defined as PD. If the Week 8 response is missing or NE but the next evaluable response is SD or better then the patient will be defined as having NPD at 8 weeks.

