8.5.5 Interim analyses

For the non HRR m population an interim analysis will be triggered when 75 patients have been recruited and assessed for at least 8 weeks, in order to assess the proportion of patients with NPD based on the Investigator assessment at 8 weeks in each of the treatment arms. With approximately 25 patients in each treatment arm, if the 80% two-sided upper CI for the proportion of patients with NPD is less than 56% (O'Shaughnessy et al 2014) and with consideration of this analysis in context with the totality of the clinical data (safety and efficacy) available, the URC may recommend to cease recruitment in this arm and no further patients will be recruited into that treatment arm in the non HRR m population. Recruitment will be paused after the 75th patient has been recruited into the population, until the AZ URC confirms the strata and which treatment arms should be reopened.

A further NPD futility interim analysis, using the same criteria, in the non *BRCAm* HRR m population may be performed, if the outcome of the interim analysis in the non HRR m population resulted in treatment arms being stopped.

As the “non HRR m ” patient population is expected to be enrolled quicker than the other patient populations, the first PFS interim analysis for patient population “non HRR m ” is triggered when 44 PFS events for the ceralasertib +olaparib vs. olaparib monotherapy pairwise comparison (65% of planned number of PFS events) have occurred in stratum C.

The second PFS interim analysis for patient populations “*BRCAm*” and “non *BRCAm* HRR m ” is triggered when 44 PFS events for the ceralasertib +olaparib vs. olaparib monotherapy pairwise comparison (65% of planned number of PFS events) have occurred in each of the two strata A and B.

The PFS interim analyses may be concurrent or separate depending on the PFS event rates in the three strata and operational requirements, so if the timings for the *BRCAm* and non *BRCAm* HRR m populations are not concurrent, separate interims may be needed for each patient population. The purpose of the interim analyses is to provide the opportunity (details will be specified in the URC Charter) for an early trigger to commence a phase III study, if the results are strong enough.

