3.3 Primary outcome measure (derivation of efficacy variables)

3.3.1 Progression-free survival

PFS is defined as the time from randomisation until the date of objective disease progression or death (by any cause in the absence of progression) regardless of whether the patient withdraws from randomised therapy or receives another anti-cancer therapy prior to progression. PFS for patients who have not progressed or died at the time of analysis will be censored at the latest date of assessment from their last evaluable RECIST assessment.

PFS will be computed as date of PFS event or censoring – date of randomisation + 1).

If, however, a patient progresses or dies after two or more missed scheduled RECIST assessments, the patient's PFS will be censored at the time of the latest evaluable RECIST assessment prior to the two missed visits.

The allowed gap between the last previous evaluable RECIST assessment and the tumour progression or death, for which the tumour progression/death will still be counted as an event, will be defined as 2 x (scheduled time between scans + allowed visit window). In details:

- If the two missed visits will occur immediately after the baseline scan then the definition of two missed visits will be calculated as 2 x (the protocol-scheduled time between scans) + the protocol-allowed visit window (since there is no need to account for an early initial visit in this case) which will be 2 x 8 weeks + 7 days + patient-specific number of days from date of randomization to date of first study treatment dose = 119 days + (patient-specific date of first study treatment dose minus date of randomization).
- If the two missed visits will occur after a post-baseline scan then the definition of two missed visits will be 2 x (the protocol-scheduled time between scans + the protocol-allowed visit window) since the previous scan may be 1 week earlier than planned and the progression visit may be 1 week later than planned.
- While a patient is in the every-8-weeks-schedule, the definition of two missed visits will be 2 x (8 weeks + 7 days) = 126 days.
- When a patient is changing from the every-8-weeks-schedule to the every-12-weeks-schedule, the definition of two missed visits will be 8 weeks + 12 weeks + 14 days = 154 days.
- While a patient is in the every-12-weeks-schedule, the definition of two missed visits will be 2 x (12 weeks + 7 days) = 182 days.

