3.4 Secondary outcome measures (derivation of efficacy variables)

3.4.1 Objective response rate

For the interim analyses, only patients fulfilling at least one of the following conditions will be included in the denominator of the ORR estimation:

- there is a post-baseline scan at least 49 days after date of randomization and up to the interim analysis data cut-off date, i.e., randomization date + 49 days \leq post-baseline scan date \leq interim analysis data cut-off date
- patient died up to the interim analysis cut-off date, i.e., death date \leq interim analysis data cut-off date.

For the final analyses there will be no such sub-setting in the denominator of the ORR estimation.

The assessment of ORR will only include tumour assessment data obtained up to

- progression
- last evaluable assessment in the absence of progression
- start of a subsequent anti-cancer therapy (note that for this analysis radiotherapy is not considered a subsequent anti-cancer therapy)

whatever occurs first.

ORR based on BICR is defined as the percentage of patients with at least one BICR-assessed visit response of CR or PR, with the denominator defined as the number of patients in the FAS (exception for interim analysis see above). If a total of at least 10 randomized patients had no measurable disease at baseline as per BICR, then an additional analysis of ORR will be conducted with the denominator defined as the subset of FAS patients with measurable disease at baseline as per BICR.

For sensitivity analysis, ORR is also defined as the percentage of patients with at least one visit response of CR or PR based on site investigator data, with the denominator defined as the number of patients in the FAS.

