3.4.6 Non-progressive disease (futility interim analysis only)

Non-progressive disease (NPD) at Week 8 based on site investigator data is defined as

- a visit response of SD, PR or CR at Week 8 (earlier visit responses of CR, PR that become PD at Week 8 or NE responses at Week 8 do not constitute NPD at Week 8)
- if the Week 8 response is missing or NE but the next evaluable response is SD or better, then the patient will be defined as having NPD at Week 8

- if an earlier visit is defined as PD then the visit response at Week 8 would also be defined as PD.

A time window around the Week 8 visit will be applied, such that any visits occurring 7 weeks or more after dosing are acceptable.

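### The Week 8 non-progression window is counted from first dose but scans are timed from randomisation, so some on-schedule stable scans are not accepted at the futility interim

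*Protocol*

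**What the plan says.** Non-progressive disease (NPD) at Week 8, by investigator assessment, is the futility measure. Protocol 8.4.1 sets its clock and denominator: "NPD will be assessed 8 weeks after dosing and is defined as the proportion of all patients dosed". The window opens at 7 weeks on the dosing clock and has no upper limit ("any visits occurring 7 weeks or more after dosing are acceptable"). SAP 3.4.6 repeats the rule ("such that any visits occurring 7 weeks or more after dosing are acceptable").

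Two further clauses in those sections matter:
- If the Week 8 response is missing or not evaluable, the patient is NPD when the next evaluable response is stable disease or better.
- Progression at an earlier visit is carried forward to Week 8. No matching clause covers an earlier stable disease or response.

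The scan schedule uses another clock. Protocol 5.1.1 sets assessments every 8 weeks (±1 week) "relative to the date of randomisation and irrespective of treatment decisions". First dose need not fall on the day of randomisation: "It is recommended that patients commence study treatment as soon as possible after randomisation, and ideally within 3 days" (Protocol Table 4, footnote a; also Section 3.5). That is a recommendation with no stated maximum.

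Protocol 8.5.5 and SAP 5.2 trigger the interim when 75 non HRRm patients have been assessed for at least 8 weeks, about 25 per arm. The criterion is an upper limit of the two-sided 80% confidence interval below 56%. A repeat in the non BRCAm HRRm population is allowed if arms were stopped: "A further NPD futility interim analysis, using the same criteria".

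**The concern.** A scan at the early edge of the protocol's own scan window can be too early for the NPD window, only because the two are measured from different dates. Once it is set aside, Week 8 is missing for that patient. The patient fails if the next scan shows progression, despite being stable at the on-schedule first scan. The patient also fails, given a denominator of all dosed patients, if no later scan exists at the cut-off. The second case is realistic because the trigger needs only 8 weeks of assessment. Neither document says explicitly how such patients are counted.

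A progression seen on an equally early scan does count, so misclassification can only lower the NPD proportion. That proportion feeds a recommendation on whether an arm keeps recruiting.

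Elsewhere the SAP treats the timing differently. The interim ORR denominator in SAP 3.4.1 asks whether "there is a post-baseline scan at least 49 days after date of randomization", and the missed-visit rule in SAP 3.3.1 adds each patient's own gap from randomisation to first dose.

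**Working it through.** The documents state no stopping count, error rate or misclassification rate for the NPD rule, so there is no planned figure to reproduce first.

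**1. Dates.** The scan window is 56 ± 7 days, that is days 49 to 63 after randomisation (15 days). SAP 3.3.1 confirms that a one-week-early scan is within schedule: "since the previous scan may be 1 week earlier than planned and the progression visit may be 1 week later than planned". With a lag of L days these are days 49 − L to 63 − L after dosing, so L of the 15 days fall before day 49: 0 at L = 0, 1 at L = 1, 3 at L = 3, 7 at L = 7. Example: dosed on day 3 and scanned on day 49 after randomisation with stable disease. The scan is 49 − 3 = 46 days after dosing and is not accepted.

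**2. Share of scans excluded (f).** Assume lags of 0, 1, 2 and 3 days are equally likely; the mean is 1.5 days.
- Scans uniform over days 49-63: f = 1.5/15 = 10%.
- Scans uniform over days 49-56: f = 1.5/8 = 18.75%.
- Scans on days 53-59: the earliest is 53 − 3 = 50 days after dosing, so f = 0.
- Same-day dosing: f = 0.

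**3. Cut-off at n = 25.** The interval method is not stated. The Clopper-Pearson upper limit is the 0.90 quantile of Beta(x + 1, 25 − x): 54.8% at x = 10 and 58.7% at x = 11. Wilson gives 52.8% and 56.7%; Wald gives 52.6% and 56.7%. All three meet the criterion at 10/25 or fewer, so one patient can move an arm across it.

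**4. Chance of meeting the criterion.** Let u be the share of excluded stable or responding patients who end as failures. The effective rate is p(1 − f·u), and the probability is P(X ≤ 10) for Binomial(25, p(1 − f·u)).

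| True NPD p | No exclusion | f = 10%, u = 0.5 | f = 10%, u = 1 |
|---|---|---|---|
| 56% | 8.0% | 0.532 → 13.1% | 0.504 → 20.1% |
| 60% | 3.4% | 0.570 → 6.6% | 0.540 → 11.4% |

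With front-loaded scans (f = 18.75%) and p = 56%, the values are 0.5075 → 19.1% for u = 0.5 and 0.455 → 36.5% for u = 1.

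On u: with exponential PFS and 56% NPD at 8 weeks, 44% of those still stable would progress in the next 8 weeks. So u = 0.5 is a plausible middle value, and u = 1 is the upper bound for a given f.

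**5. At the design assumption.** Protocol 8.2 assumes a 5-month median on olaparib in this stratum. Exponential NPD at 56 days (1.84 months) is 0.5^(1.84/5) = 77.5%. The chance is then about 0.01% without exclusion and 0.2% with f = 10% and u = 1 (effective rate 0.6975).

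**The case against.** The case for leaving the rule alone has real substance.

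- **The anchor is defensible.** NPD is defined among dosed patients at 8 weeks after dosing, so window and denominator share one clock. The ORR rule in SAP 3.4.1 concerns randomised patients and is a different measure. This stands as a reason for the choice, but it does not explain why a scan done on schedule should be discarded.
- **The asymmetry is partly natural.** Progression before Week 8 settles the status at Week 8; stable disease before it does not. That holds for a scan well before Week 8, and less so for one inside the Week 8 scan window.
- **Scan timing may be benign.** Protocol Table 4 places tumour assessment with the Day 1 cycle visits (±3 days). Cycle 3 Day 1 is 56 days after first dose, so scans tied to it fall about 53-59 days after dosing and none is lost. Footnote e still permits the full ±1 week from randomisation.
- **The next-response clause rescues many patients.** Those recruited early can have a Week 16 scan by the cut-off, so counting every excluded patient as a failure is an extreme.
- **The rule is advisory.** The committee may recommend stopping, weighing all the clinical data, and its first set of outputs includes investigator PFS and best response. The probabilities above concern meeting a criterion, not closing an arm.
- **The stratum C interim appears to be past.** SAP 5.2 reports an April 2019 decision.

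A reader might go further and infer that early stable scans generally count as failures, or that the window explains the closure of the AZD1775 arm. The documents support neither. Only scans in the first L days of the window are affected. SAP 5.2 sets the April 2019 decision beside a safety recommendation covering all three populations, Protocol 1.2.2 cites toxicity and no suggestion of benefit, and no NPD counts are given.

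**Conclusion.** The mismatch is real and appears in both documents: a scan that complies with the schedule can be refused as a Week 8 scan, and the resulting error can only lower NPD. Its size is uncertain because neither the dosing lag nor the spread of scan dates is given. It ranges from nothing (same-day dosing, or scans near day 56) to a rise from 8% to about 13% in the chance of meeting the criterion at a true NPD of 56%, with 20% as the upper bound, when lags are 0-3 days and scans are even across the window. Scans concentrated before the due date would make it larger. It matters only for arms close to the 56% benchmark, which under exponential PFS means a median of about 2.2 months. At the assumed 5 months it is negligible.

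The point remains live because Protocol version 7.0 keeps the rule and still permits a non BRCAm HRRm interim on the same criteria. Reading the stratum C result also depends on the definition.

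**What to change.** In Protocol 8.4.1 and SAP 3.4.6, define the Week 8 window on the scan schedule: accept visits 49 days or more after randomisation, as SAP 3.4.1 does for interim ORR. No on-schedule scan is then excluded at any lag. Keep all dosed patients as the denominator, and state how a patient with a missing or non-evaluable Week 8 scan and no later scan at the cut-off is counted.

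Use the revised window for any non BRCAm HRRm interim, and re-tabulate stratum C under it to see whether any arm changes side of 10/25.

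The cost is one phrase in each document, one sentence on missing scans and a different date variable in one program; no new data are needed. There are two small downsides. A patient dosed late is judged after less than 7 weeks on treatment (dosed on day 10 and scanned on day 49 gives 39 days). The second interim would also differ slightly from the first unless stratum C is re-tabulated.

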8.4.2 Secondary outcome measures (Calculation or derivation of safety variables)

Safety and tolerability will be assessed in terms of AEs, deaths, laboratory data, vital signs, ECG data and ECOG PS. These will be collected for all patients.

Adverse events

AEs (both in terms of Medical Dictionary for Regulatory Activities [MedDRA] preferred terms and CTCAE grade) will be listed individually by patient.

Any AE occurring within 28 days of discontinuation of IP will be included in the AE summaries. Any events in this period that occur after a patient has received further therapy for cancer (following discontinuation of IP) will be flagged in the data listings.

Other significant AEs (OAEs)

During the evaluation of the AE data, an AstraZeneca medically qualified expert will review the list of AEs that were not reported as SAEs and AEs leading to discontinuation. Based on the expert's judgement, significant AEs of particular clinical importance may, after consultation with the Global Patient Safety Physician, be considered OAEs and reported as such in the CSR. A similar review of laboratory/vital signs (pulse and BP)/ECG data will be performed for identification of OAEs.

Examples of these could be marked haematological and other laboratory abnormalities, and certain events that lead to intervention (other than those already classified as serious), dose reduction or significant additional treatment.

8.4.3 Safety outcome measures (Calculation or derivation of pharmacokinetic variables)

Given the sparse PK schedule, the PK parameters will be derived using population PK modelling. The results of any such analyses will be reported separately from the CSR.

8.5 Methods for statistical analyses

All efficacy analyses will be performed on the FAS. Results of statistical analyses will be presented using 90% CIs and 2-sided p-values.

Pairwise comparisons between the ceralasertib + olaparib vs. olaparib monotherapy, AZD1775+olaparib vs. olaparib monotherapy and ceralasertib + olaparib vs. AZD1775+olaparib will be generated for each endpoint.

Following the decision of the ISRC to close recruitment to the AZD1775 + olaparib arm, the study will only be sized to detect a difference for the ceralasertib + olaparib vs olaparib monotherapy comparison, although all the available data across all 3 arms, where possible, will be used in the statistical models.

As the starting dose of the AZD1775+Olaparib arm was refined during the study, for any comparisons including the AZD1775+olaparib arm, all AZD1775+olaparib patients regardless of their starting dose will be included in the analyses. Additional sensitivity analyses may be carried out which only including those patients AZD1775+Olaparib patients who start treatment on the revised starting dose.

The assignment of a patient to each of the populations will be based on the values entered into IVRS at randomisation, even if it is subsequently discovered that these values were incorrect or not confirmed by the central FMI assay. If there are any patients who were wrongly assigned, a sensitivity analysis may be carried out with patients in the population they should have been assigned to.

The stratification in the statistical modelling will be based on the values entered into IVRS at randomisation, even if it is subsequently discovered that these values were incorrect. If there are any patients who were mis-stratified, a sensitivity analysis will be carried out using the (correct) baseline data collected in the eCRF.

